### **23.2. Hepatitis Testing**

Treatment with TDF/FTC or its components or congeners in participants with chronic active hepatitis B (Hepatitis B surface antigen (HBsAg) positive) has been associated with flares of hepatitis upon discontinuation of treatment. Such participants will be referred to appropriate medical care for monthly liver function testing subsequent to treatment completion and/or consideration of ongoing Hepatitis B treatment. HBsAg negative participants will be referred for appropriate vaccination.

### **23.3. Serum Creatinine**

Serum creatinine will be checked at screening to determine appropriate TDF/FTC dosing, and then again at Weeks 4, 12, 24, 36 and 48.

### **23.4. Liver Function Tests**

AST (SGOT), ALT (SGPT), Total Bilirubin (TBIL), and alkaline phosphatase will be checked at baseline for all participants, and in a symptom-directed fashion as needed.

### **23.5. Complete Blood Count**

Hemoglobin, hematocrit, white blood cell count and platelet count will be checked at baseline for all participants, and in a symptom-directed fashion as needed.

### **23.6. Pregnancy testing**

Urine beta HCG will be performed to assess for pregnancy at screening, baseline, weeks 4, 12, 24, 36, and 48, and in a symptom-directed fashion.

## **24. PLASMA COLLECTION**

Plasma will be collected and stored at Weeks 4, 12, 24, 36 and 48. If seroconversion to HIV occurs, plasma samples will be run for HIV-1 RNA (viral load) and genotyping. These specimens may also be used for safety labs, or for tests whose needs become apparent during the course of this study. Additional whole blood will be collected at the visit seroconversion was detected and 24 weeks post seroconversion to determine viral reservoir size and immune responses.

## 25. DRIED BLOOD SPOT COLLECTION

Blood will be collected for and spotted onto Whitman Protein Saver Card for DBS analyses. All specimens will be stored at -80C. DBS samples available from weeks 4, 12, 24 and 36 will be sent to the University of Colorado lab once weekly for real-time analysis.

## 26. POST-TRIAL ACCESS TO PREP

During study conduct, the team will initiate discussions about continuation mechanisms at either the 24- or 36-week visit to prepare for the 48-week transition off study, allowing ample time for discussion of intentions to continue PrEP post-study, assessment of insurance status, choice of healthcare location and provider, and prescription benefits optimization.

The team will conduct a phone call follow-up of all participants 3 months post-study completion to determine post-trial access to and use of PrEP. Survey content will be based on an instrument developed by the PrEP Demo Project based in San Francisco (77). Information will be collected including current medical access and care, HIV testing, interest in remaining on PrEP, access to and use of PrEP, gaps in PrEP coverage, monthly cost, barriers to getting PrEP, and changes in HIV prevention strategies. Surveys may be conducted in person, via internet, or over the phone.

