#### 4. STUDY SCHEMA

- Design: AEGIS is an open-label single-arm longitudinal clinical trial to estimate medication adherence and retention in a PrEP HIV prevention program that implements a combination intervention strategy that uses text-messages (iTAB) and a staged adherence counseling support strategy titrated from real-time drug levels in women at-risk for HIV acquisition.
- Duration: Each participant will be on PrEP with medication adherence support for 48 weeks after enrollment with a post study follow-up at 60 weeks. The primary endpoint will be measured at 48 weeks.
- Sample Size: A total of 135 participants will be enrolled (50 at CCTG sites and 85 at the LAC-PATH site).
- Study Population: Eligible participants will include HIV-uninfected cis-gender women at least 18 years of age and who are at risk for HIV acquisition.
- Intervention: All participants will be given PrEP with tenofovir disoproxil fumarate (TDF) + emtricitabine (FTC) fixed dose combination prescribed to be taken once daily. All participants will receive the combined intervention of iTAB text messaging adherence reminders and intensive Next Step Counseling (iNSC). The iTAB system consists of daily, personalized, automated 2-way text messages to maintain adherence and retention, and iNSC is a brief, strengths-based discussion initiated at each clinic visit, typically with delivery of negative HIV-test results, focused on promotion of sexual health protection through behavioral and biomedical (adherence) strategies. Participants that have a low intracellular tenofovir diphosphate (TFV-DP) concentration will receive escalated, targeted adherence support (see study schema). All participants will receive access to PrEP in accordance with standardized comprehensive methods of prescribing and clinical assessments that include safety monitoring as well as regular HIV and sexually transmitted infection (STI) screening.
- Regimen: TDF 300 mg + FTC 200 mg fixed dose combination will be given orally once daily starting at the baseline visit (month 0) and continued throughout the study.

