### **16.3. Duration of Therapy**

TDF/FTC should be taken daily for 48 weeks (336 days). Participants may receive study treatment until their last study visit. Further plans for continued availability of TDF/FTC for PrEP after the first 48 weeks will be determined based on the results of the current pilot demonstration study.

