### **Secondary Objectives:**

To describe the characteristics of women seeking PrEP, a descriptive analysis will be performed for the following secondary endpoints:

- PrEP awareness and acceptability prior to study enrollment
- Perceived barriers and facilitators to PrEP use
- HIV knowledge pre- and post-study

Implementation secondary outcomes will include:

- Acceptability and feasibility of an HIV prevention program with a multimodal, intensive adherence package for PrEP delivery defined on a Likert scale
- Retention in an HIV prevention program that includes PrEP defined by making study visit
- Safety and tolerability of daily TDF/FTC given for PrEP including discontinuation for any adverse event, serious adverse events and adverse events (grade 2 or higher)
- HIV incidence in the observed cohort of PrEP users
- Frequency of clinically significant resistance among seroconverters

Additional sensitivity regression modeling will be performed for the factors associated with loss to follow up and discontinuation of TDF/FTC. Factors will included change in perceived and actual risk of HIV acquisition, fear of disclosure, demographics, socioeconomic status, social characteristics (e.g., medical mistrust, non-English language, cultural factors), co-occurring health problems or issues (e.g., untreated mental illness, ongoing substance use, violence, trauma), and low health/HIV and system literacy.

Risk compensation during study will be assessed by changes in the incidence of STIs (chlamydia, gonorrhea, HSV-2 and syphilis) during study and self reported sexual risk behavior over time by number of sexual partners (by HIV status) and number condomless sex acts.

All descriptive results will be reported as point estimates (mean or odds ratios as appropriate) and interval estimates (95% confidence intervals, interquartile ranges). All tests of significance for the secondary outcomes will be 2-sided and no adjustments will be made for multiple comparisons. A p-value of 0.05 will be considered statistically significant. Statistical analysis will be conducted using the statistical software R 3.1.1 ([www.r-project.org](http://www.r-project.org)).

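### No scheduled safety assessment follows week 48, so a hepatitis flare in an HBsAg-positive woman who stops TDF/FTC then would reach the safety counts only through an unscheduled or outside report

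*Combined protocol and SAP*

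**What the plan says.** **Treatment period.** Section 16.3 sets 48 weeks (336 days) of daily drug and adds: "Participants may receive study treatment until their last study visit". Section 16.4 makes the last dispensing a 12-week supply at week 36.

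**Who is treated.** Table 1 tests HBsAg at screening. Neither section 13 nor section 14 makes a positive result a bar to entry.

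**The named harm.** Section 23.2 says that TDF/FTC in participants with chronic active hepatitis B "has been associated with flares of hepatitis upon discontinuation of treatment". It continues: "Such participants will be referred to appropriate medical care for monthly liver function testing subsequent to treatment completion", and also mentions that ongoing hepatitis B treatment may be considered. It does not say whether results from that outside care come back to the study.

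**Liver tests within the study.** Under section 23.4 these "will be checked at baseline for all participants, and in a symptom-directed fashion as needed". Table 1 marks them at baseline only.

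**After week 48.** Table 1 has no visit after End of Study. Section 4 gives each participant 48 weeks on PrEP "with a post study follow-up at 60 weeks". Section 26 gives that contact's purpose: "The team will conduct a phone call follow-up of all participants 3 months post-study completion to determine post-trial access to and use of PrEP". The listed content covers medical access and care, HIV testing, interest in PrEP, its access and use, gaps, cost, barriers and changes in prevention strategy.

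**Safety outcome.** Section 30.2 lists "Safety and tolerability of daily TDF/FTC given for PrEP including discontinuation for any adverse event, serious adverse events" and adverse events of Grade 2 or higher. Section 27.1.1 makes Grade 2 or higher clinical and laboratory abnormalities reportable and counts hospitalization as serious.

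**The concern.** The harm that section 23.2 names is one of stopping, not of taking, the drug. For a woman who completes treatment and then stops, the time at risk begins as scheduled safety observation ends. A flare in the following weeks, even one serious enough for hospitalization, has no scheduled contact or data source through which it would be recorded.

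What is at stake is the reading of the safety summary. If it reports no hepatitis events among 135 women, a reader may take that as evidence about post-treatment flares. For women who stopped at week 48, it would mainly reflect that nobody was scheduled to ask. The point concerns data capture and reporting. It does not question the care of these women, which section 23.2 covers by referral.

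**Working it through.** **1. Timeline, from the plan's own figures.**
- Treatment: 336 / 7 = 48 weeks.
- Supply dispensed (16.4): 4 + 8 + 12 + 12 + 12 = 48 weeks.
- Last contact: 48 + 12 = 60 weeks, which agrees with section 26 if three months is read as 12 weeks.
- Scheduled safety observation after a last dose at week 48: 48 − 48 = 0 weeks. A contact exists 12 weeks later, but no safety item is listed for it.
- Early permanent stoppers stay on the schedule (28.2). A stop at week 12 leaves 48 − 12 = 36 weeks of scheduled visits, and a stop at week 36 leaves 48 − 36 = 12 weeks. Liver tests at those visits are symptom-directed only, so a flare without symptoms could be missed.

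The plan's only statistical design figure, 90% ± 6% with 100 women, reproduces: 1.96 × √(0.9 × 0.1 / 100) = 5.88 points. It has no bearing on this point.

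**2. How many women might be affected.** The documents give no HBsAg prevalence, so p is an assumption, ranged widely. Expected number = 135 × p; chance of at least one = 1 − (1 − p)^135.

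| Assumed p | Expected HBsAg-positive | Chance of at least one |
|---|---|---|
| 0.2% | 0.27 | 24% |
| 0.5% | 0.68 | 49% |
| 1% | 1.35 | 74% |
| 2% | 2.7 | 93% |
| 5% | 6.75 | 99.9% |

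These are women, not flares, and those who stop at week 48 are some unknown part of them.

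**3. What a zero count could say.** Let n be the number of HBsAg-positive women who stop, f the flare risk and c the probability that a flare is recorded (f and c are both assumed). The chance of recording none is (1 − f × c)^n.
- If nothing is captured after week 48 (c = 0), this is 1 whatever f is.
- With n = 3 and f = 0.25: for c = 0.5, (1 − 0.125)^3 = 0.67; for c = 1, (1 − 0.25)^3 = 0.42.

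**4. Precision with full capture.** With zero events in n women, the one-sided 95% upper bound on the flare risk is 1 − 0.05^(1/n).
- n = 1: 95%
- n = 3: 63%
- n = 7: 35%
- n = 135, if all enrolled women were wrongly used as the denominator: 2.2%

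Full capture therefore cannot give a precise flare rate. The contrast with the last line shows why the denominator has to be stated.

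**The case against.** A reader might infer that post-treatment flares cannot enter the safety results at all and that any zero count is meaningless. The documents do not support that, for four reasons.

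- Section 28.2 keeps women who stop permanently before week 48 on the schedule of evaluations, so part of their time after stopping is observed.
- Section 27.1.1 calls for an unscheduled visit with liver tests for intolerance, including jaundice or abdominal pain.
- Section 29.4 starts adverse event monitoring at consent and states no end, so a late event that is reported is not barred.
- Week 48 ends study supply, not necessarily treatment. Section 26 prepares for continued PrEP and section 23.2 allows for ongoing hepatitis B treatment.

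Nor can capture between weeks 48 and 60 be put at nil. The list in section 26 is introduced as inclusive, its first item is current medical access and care, and the source instrument is not reproduced. Operational detail is often deferred to the MOPS, and section 30 says a later, more detailed SAP will take precedence.

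It is also fair to say that the affected group may be empty, that the safety objective is descriptive and could be read as on-treatment safety, and that the adherence outcome is untouched.

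These points narrow the concern but do not remove it. The routes named depend on a woman coming back, or being reported, after her last scheduled visit. An adverse event window with no stated end means that two analysts could treat the same week-52 hospitalization differently. A small group makes its denominator more important, not less.

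**Conclusion.** The point holds in limited form. No scheduled safety assessment follows week 48, the week-60 survey lists no adverse event item, and no return route is stated for the referred liver results. For HBsAg-positive women who stop at week 48, a zero flare count would be uninformative unless unscheduled or outside reports reach the study. For early stoppers it carries some information, limited by symptom-directed testing. Women still on drug are not yet at risk.

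The size is uncertain: about 0.3 to 7 of 135 women under an assumed prevalence of 0.2% to 5%. The documents give neither a prevalence nor a flare risk, so the number of missed events cannot be estimated. It would go too far to conclude that the plan leaves these women without care or shuts late events out. The defect is an undefined window, an unused contact and a missing denominator in a secondary safety summary. It is worth correcting because the protocol itself names the harm and the correction is cheap.

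**What to change.** **Section 26.** For women HBsAg-positive at screening, add to the existing week-60 contact:
- whether and when TDF/FTC was stopped;
- any hepatitis diagnosis or hospitalization since week 48;
- results of liver tests done in referred care, where the woman gives written permission.

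**Section 30.2, carried into the formal SAP.** State that the adverse event and serious adverse event window runs to week 60 for these women. Report post-stopping hepatitis events on a separate line, with the number of HBsAg-positive women who stopped and were followed as the denominator.

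**Cost.** A few questions in a contact already planned for every participant, a permission request for a small number of women, and one table line. No new visit, test or staff is needed. The downside is that events between weeks 48 and 60 will be partly self-reported where outside results are not released, and precision will stay poor. Clinical monitoring stays as the protocol sets it.

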## 27. CLINICAL MANAGEMENT ISSUES

### 27.1. Toxicity Management

#### 27.1.1. General

In the event of intolerance, including but not limited to rash, nausea, vomiting, clinical jaundice, or abdominal pain, an “unscheduled visit” should be made in which a directed clinical assessment and laboratory evaluations including creatinine, liver function tests, and complete blood count are performed. Alternative regimens may not be substituted.

Only toxicities related to study medication provided through this study (TDF/FTC) will be considered in the toxicity management section. The grading system is located in the Division of AIDS Table for Grading the Severity of Adult and Pediatric Adverse Events (DAIDS AE Grading Table), Version 2.0, November 2014, available at the DAIDS RCC Web Site: <http://rsc.tech-res.com>. Grade 1 creatinine elevations will have an expanded definition: In addition to those defined as having Grade 1 creatinine elevations by DAIDS AE Table, the Grade 1 definition will include A) those whose creatinine increased to 1.5x the baseline value (baseline value will be defined as the average of screening and enrollment for the participant) and B) estimated creatinine clearance of <50 ml/min (calculated using Cockcroft- Gault).

Adverse events will be reported for Grade 2 and above clinical and laboratory abnormalities. In addition, all bone fractures and all creatinine elevations will be reported. Serious adverse events (SAEs) will be defined in accordance with the ICH, as any untoward medical occurrence that, at any dose, results in death, is life-threatening, requires inpatient hospitalization or prolongation of existing hospitalization, or results in persistent or significant disability/incapacity.

All Grade 1 or 2 adverse events may be managed according to the discretion of the provider, except as noted below.

Grade 3 adverse events, if asymptomatic and not thought to be attributable to study medication, may be managed conservatively with continuation of TDF/FTC treatment.

All Grade 3 symptomatic and all Grade 4 (regardless of symptomatology) events should prompt cessation of TDF/FTC therapy, with weekly monitoring until resolution to  $\leq$  Grade 2. If a clear alternative explanation for the Grade 4 adverse event exists, TDF/FTC may only be continued with the approval of the Protocol PI. Once the AE has regressed to  $\leq$  Grade 2, the participant may be rechallenged with TDF/FTC at the discretion of the provider. Any recurrence of the AE should prompt permanent medication discontinuation.

#### 27.1.2. Impaired Creatinine Clearance

Any participant with a calculated creatinine clearance (CrCl)  $<60$  mL/min should have the value confirmed within 14 days. For those participants with a confirmed (i.e. two consecutive) reduction in CrCl to  $<60$  mL/min, TDF/FTC should be discontinued. If the site investigator determines that another condition caused the decrease in CrCl, then TDF/FTC may be restarted if approved by the protocol PI. Participants should be followed as medically indicated (at least weekly) until the serum creatinine returns to Grade  $\leq 2$  or baseline.

#### 27.1.3. Nausea (with or without vomiting) and/or Diarrhea

Although common, nausea following initiation of therapy with study medications usually subsides or resolves during the first few weeks of treatment.

With the onset of Grade  $\geq 1$  nausea, advise participants to take study medications with food. Participants may also be treated as needed with anti-emetics given orally or by suppository.

In participants with persistent nausea, consideration should be given for evaluation of pancreatitis, hepatitis, hyperlactatemia/lactic acidosis, or hypercalcemia with evaluation for each if clinically indicated.

For Grade 1 or 2 diarrhea, therapy should be continued with symptomatic treatment with antimotility agents. If Grade  $\geq 3$  diarrhea occurs and is unresponsive to antimotility agents, and an alternative etiology (e.g., infectious diarrhea) is not established, all study medications should be interrupted until resolution of diarrhea to Grade  $\leq 2$  or return to baseline. If Grade  $\geq 3$  diarrhea recurs upon the resumption of the study medications, all study medications should be discontinued permanently.

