**28. CRITERIA FOR DISCONTINUATION**

**28.1. Temporary Medication Interruption**

Attempts should be made to avoid temporary interruption.

Symptoms should be managed aggressively and proactively in an attempt to avoid discontinuation, provided there is no laboratory evidence of toxicity and any symptoms are Grade 1 or 2. In the event of symptomatic Grade 3 or any Grade 4 toxicity, TDF/FTC should be discontinued immediately, the only exception being a toxicity indisputably not attributable to TDF/FTC administration, with the permission of the protocol PI.

In the event of inadvertent discontinuation due to missed appointments, loss of medication, or other unforeseen circumstances, treatment should be resumed as rapidly as possible. Treatment should ONLY be reinstated in the absence of signs/symptoms of PHI (Table 1 above).

If the amount of time since last dosing of TDF/FTC exceeds 14 days when the participant wishes to reinitiate PrEP, a negative rapid HIV EIA and HIV VL should be documented PRIOR to PrEP reinitiation. If a serum creatinine has not been performed for study purposes within the past 30 days, serum creatinine too should be repeated (and Creatinine Clearance calculated and documented) prior to medication re-initiation.

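### The Grade ≥3 diarrhea rule in section 27.1.3 does not agree with the general stopping rules in sections 27.1.1 and 28.1, and no sentence says which governs

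*Combined protocol and SAP*

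**What the plan says.** Three places in the protocol bear on a woman with diarrhea of Grade 3 or above.

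- **Section 27.1.3 (diarrhea).** Interruption depends on whether an event of Grade 3 or above meets this wording: "diarrhea occurs and is unresponsive to antimotility agents, and an alternative etiology (e.g., infectious diarrhea) is not established, all study medications should be interrupted". Two conditions are joined: failed antimotility treatment, and no other cause found. PI permission is not mentioned.
- **Section 27.1.1 (general toxicity rules).** "All Grade 3 symptomatic and all Grade 4 (regardless of symptomatology) events should prompt cessation of TDF/FTC therapy". The exception reads: "If a clear alternative explanation for the Grade 4 adverse event exists, TDF/FTC may only be continued with the approval of the Protocol PI". It is written for Grade 4 only.
- **Section 28.1 (temporary interruption).** The rule covers Grade 3 events with symptoms and Grade 4 events of any kind: "TDF/FTC should be discontinued immediately, the only exception being a toxicity indisputably not attributable to TDF/FTC administration, with the permission of the protocol PI".

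Two further sentences in section 27.1.1 affect how these fit together. One limits scope: "Only toxicities related to study medication provided through this study (TDF/FTC) will be considered in the toxicity management section". The other contains the only wording that points forward to exceptions: "All Grade 1 or 2 adverse events may be managed according to the discretion of the provider, except as noted below".

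On the analysis side, section 30.2 runs the primary adherence analysis in women who are on PrEP, censoring those on temporary or permanent discontinuation. It also lists stopping for an adverse event among the safety outcomes. Section 11 places the study at five clinical sites.

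**The concern.** A stopping rule should give one answer for one event. Here a clinician who opens the diarrhea subsection and a clinician who opens the general rules can reach different answers for the same woman. No sentence ranks the texts.

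The first thing at stake is participant safety and consistent conduct across five sites. The second is the analysis. Whether drug is stopped decides whether a woman can be counted as discontinued for an adverse event. It may also decide whether she is censored from the as-treated adherence proportion.

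**Working it through.** **Step 1. Compare the rules case by case.** Section 27.1.3 sets two conditions, so there are four cases of Grade ≥3 diarrhea.

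| Case | Responds to antimotility agents? | Other cause established? | 27.1.3 | 27.1.1 | 28.1 | In conflict? |
|---|---|---|---|---|---|---|
| 1 | No | No | Interrupt | Stop | Stop at once | No |
| 2 | Yes | No | Interruption not called for | Stop | Stop at once | Yes, directly |
| 3 | No | Yes | Interruption not called for; no permission mentioned | Grade 3: stop, no exception. Grade 4: may continue with PI approval | May continue only if clearly unrelated to drug beyond dispute, with PI permission | Yes, on permission and standard of attribution |
| 4 | Yes | Yes | As case 3 | As case 3 | As case 3 | As case 3 |

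The table treats Grade 3 diarrhea as symptomatic, since diarrhea is itself a symptom. Section 27.1.1's allowance for asymptomatic Grade 3 events therefore does not apply. Grade 4 is stopped regardless of symptoms.

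**Step 2. Look for a sentence that makes 27.1.3 an override.** The forward reference in 27.1.1 is attached to Grade 1 and 2 events, so it does not cover this. Section 28.1 describes its exception as the only one. The same section speaks of managing symptoms to avoid stopping only where they are Grade 1 or 2. No override was found.

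**Step 3. Size of the effect on counts.** The conflict is one of logic and no planned figure is wrong because of it. The documents give no rate of Grade ≥3 diarrhea, so the rates below are assumptions.

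- Planned precision (section 30.1): 1.96 × √(0.9 × 0.1 / 100) = 5.88%, which reproduces the stated ±6%.
- One woman in the safety proportion: 1/135 = 0.74 percentage points.
- Expected women with an event, assuming 0.5% to 5% of 135: 135 × 0.005 = 0.7, to 135 × 0.05 = 6.8.
- Chance of at least one such woman: 1 − 0.995^135 = 49%, to 1 − 0.95^135 = 99.9%.
- As-treated proportion, starting from 90 of 100 women above the cutoff:
  - One woman censored: 89/99 = 89.9% if she was above the cutoff, 90/99 = 90.9% if below.
  - Five censored: 85/95 = 89.5% if all were above, 90/95 = 94.7% if all were below. The half-width is then 1.96 × √(0.09/95) = 6.0%.

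These counts are upper bounds on the assumed rates, because case 1 events are stopped under every section.

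**The case against.** The strongest reply has four parts.

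- **Specific over general.** Section 27.1.1 is headed as general and the subsections after it are event-specific, so reading the diarrhea text as governing is ordinary practice. That is a reasonable reading, but the protocol does not state it, and section 28.1's claim to a single exception stands against it.
- **27.1.3 never says drug continues.** This is correct: continuation follows only by implication. A site could treat 27.1.3 as silent and fall back on the general rules. The two conditions would then have almost no function, so a site that acts on them is not misreading the text.
- **The scope sentence.** It limits the toxicity section to drug-related events, so diarrhea with an established infectious cause arguably falls outside it. This softens cases 3 and 4. It does not touch case 2, and section 28.1 lies outside that section and still asks for PI permission.
- **Oversight.** Section 32 provides for expert consultation when attribution is unclear or toxicity requires stopping. Section 29.4 has the Protocol Chairs review Grade ≥2 signs and symptoms monthly. Unnoticed divergence between sites is therefore less likely, but the text still gives two answers.

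A reader might infer that every Grade 3 or 4 diarrhea event is affected, that sites will in fact diverge, and that the safety counts will vary as a result. The documents do not support this. Case 1 is handled alike everywhere. Divergence is possible but not shown. Counts of Grade ≥2 and serious adverse events do not depend directly on which stopping rule a site follows.

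**Conclusion.** The inconsistency is real and limited. It is direct for Grade ≥3 diarrhea that responds to antimotility agents with no other established cause. Where another cause is established it is partial, concerning PI permission and the standard of attribution. It is absent for unresponsive diarrhea with no other cause. The two general rules also differ from each other: 27.1.1 writes its exception for Grade 4 only, while 28.1 applies its own to symptomatic Grade 3 as well.

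The effect on results is probably small. It can reach discontinuations for adverse events, although section 30.2 does not say whether a short interruption counts as one. It can reach as-treated censoring, although an interruption that resolves between the five assessment weeks need not remove a woman from any of them. One censored woman moves a 90% proportion by less than 1 point against a planned ±6%. Five would move it by 0.5 points down to 4.7 points up, and only the extreme arrangement gives the larger figure. All event counts rest on an assumed rate.

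The reason to act is a single, consistent safety instruction, more than the arithmetic. The manual of procedures and any separate SAP were not available and might already settle the matter.

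**What to change.** Reconcile sections 27.1.1, 27.1.3 and 28.1. State which text governs Grade 3 diarrhea and which governs Grade 4, whether PI permission is needed to continue drug, and what standard of attribution applies when another cause is established. A cross-reference in each section to the governing one would prevent the same question arising again. The clinical content is for the sponsor to decide.

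It would also help to state in the SAP whether a temporary interruption counts as a discontinuation for an adverse event.

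The cost is a protocol clarification and a short notice to the five sites. Sample size, visits and data collection do not change.
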